9.7 Statistical methods planned in the protocol and determination of sample size

This document contains details of the statistical methods which will be used in the phase IIIb clinical trial CLCZ696B2317. The purpose of this study is to collect safety and tolerability data on LCZ696 in former PARADIGM-HF patients receiving open-label investigational drug. For each country, the study has a minimum duration of 12 months.

9.7.1 Statistical and analytical plans

The planned analysis is described in section 9 of the study protocol. All data analyses will be performed using SAS® statistical software (Version 9.3) unless otherwise noted. To ensure consistency across studies within the project, the RAP refers to the CSU harmonization MAP for heart failure (version number Final 1.0) and can be found in Novartis Clinical Research Documentation and Information system (CREDI)

9.7.1.1 Analysis sets

The following analysis populations will be defined for statistical analysis:

- **Enrolled set (ENR)** – All patients who signed the open-label study informed consent.
- **Safety set (SAF)** – All patients who enrolled in the study and received at least one dose of open-label study medication.

All cases of prospectively defined protocol deviations will be identified prior to clinical database lock and entered into a dedicated data panel as part of the locked database.

All exceptional cases and problems and the final decisions on the allocation of patients to populations will be fully defined and documented before database lock and will be fully identified and summarized in the clinical study report according to ICH E9.

Criteria defining protocol deviations are referenced in the Data Review Plan (DRP).

Table 9-1 Rules for subject classification in the analysis sets based on protocol deviations and non-protocol deviation classification criteria

Analysis set	PD severity codes that cause a subject to be excluded	Non-PD criteria that cause a subject to be excluded
Enrolled set	INCL01 Written informed consent missing	NA
Safety set	WITH01 Subject withdrew consent but continued to receive study medication. Data after withdrawal date will be excluded from SAF.	Subject did not receive study medication

9.7.1.2 Subject disposition, background and demographic characteristics

9.7.1.2.1 Subject disposition

Patients who signed the CLCZ696B2317 study informed consent but do not meet all of the enrollment requirements at Visit 1 are considered screening failures.

The number and percent of patients in the enrolled set who discontinue the study will be summarized. Discontinuations will be further summarized by reasons.

The reason for screen failure will be tabulated and listed. For patients who have re-screening visits, the reason for screen failure in the last screening visit will be reported.

The patients' center and patient numbers in this study and their corresponding center and patient numbers in PARADIGM-HF study (i.e., LCZ696B2314) will be listed.

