6.1 Information to be collected on screening visit (Visit 1)

Please refer to [Table 6-1](#) Assessment Table for the information to be collected during the Screening visit. If a patient is not eligible for enrollment, the investigator may consider re-screening the patient at a later time if he/she believes that the patient's condition has changed and may potentially be eligible. In this case, a completely **new patient number will be allocated to the subject** and he/she will need to re-perform all Visit 1 assessments. A patient may be re-screened for enrollment in this protocol up to two additional times with a minimum of 2 weeks between re-screening visits. The patient must provide new written informed consent before each time they are to be re-screened.

For these patients that are considered screening failures only baseline characteristics, demographic information, and the Screening Log entry with the reason for screen failure should be completed on the eCRF.

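### Study discontinuation is reported as a percentage of all consent signers, including screen failures who never took LCZ696, so the only planned all-cause discontinuation rate by reason is not a rate among treated patients

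*SAP*

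**What the plan says.** SAP 9.7.1.2.1 plans the disposition summary in ENR: "The number and percent of patients in the enrolled set who discontinue the study will be summarized". The breakdown by reason follows from the same summary.

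SAP 9.7.1.1 defines ENR as "All patients who signed the open-label study informed consent". Table 9-1 lists one ground for exclusion from it, "INCL01 Written informed consent missing", and no criterion outside protocol deviations. SAF is narrower: "All patients who enrolled in the study and received at least one dose of open-label study medication".

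SAP 9.7.1.2.1 also describes people who signed consent "but do not meet all of the enrollment requirements at Visit 1 are considered screening failures". Their reasons for failing are tabulated separately, using the last attempt for anyone screened more than once.

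On re-screening, Protocol 6.1 says "A patient may be re-screened for enrollment in this protocol up to two additional times". Each time a "new patient number will be allocated to the subject", and "The patient must provide new written informed consent before each time they are to be re-screened".

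Protocol 5.5.9 treats permanent discontinuation of LCZ696 as withdrawal from the study.

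**The concern.** Tolerability is part of the primary objective (Protocol 2.1 and 9.4). Because stopping the drug for good means leaving the study, the disposition table doubles as the all-cause drug-discontinuation table. A reader will want from it the share of treated patients who stopped, and why. With ENR as the denominator it answers a different question, since people who were never dosed are counted among those at risk of stopping.

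No other planned output fills the gap. The tables in SAP 9.7.1.6.1 cover only discontinuations attributed to adverse events. The last-recorded-dose table in SAP 9.7.1.5.2 shows how many patients are at dose level 0, but it gives no reasons, and level 0 is also the code for an interruption. Exposure (SAP 9.7.1.5.1) is summarised in SAF, and baseline data (SAP 9.7.1.2.2) in SAF and also ENR. Disposition uses ENR alone.

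The set's name adds to the problem. Protocol 5.5.13 and SAP 9.7.3 use enrolment to mean entry of eligible patients, so a reader could take the percentage as based on entrants.

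**Working it through.** **The nearby stated figure.** The plan gives no discontinuation, screen-failure or re-screening rate. It does give the expected enrolment of 5,000 as about 59% of the core study (SAP 9.7.3), and Protocol 1.1 gives the core size as 8,436. 5,000 / 8,436 = 59.3%, so that figure reproduces. I use 5,000 as the number treated.

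**Who is in the denominator.** Consent is the only entry condition for ENR and missing consent the only exclusion. A screen failure has by definition signed consent. Screen failures are therefore in ENR, and SAF leaves them out because it needs a dose.

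**Inputs for the size.**
- T = 5,000 treated.
- d = discontinuation rate among treated patients; assumed 20%.
- s = share of ENR who are screen failures; assumed 5%, 10% or 20%.
- For simplicity, everyone in ENR is either treated or a screen failure.

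Then ENR = T / (1 − s), and the number of treated patients who discontinue is dT = 1,000.

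**Case A: screen failures in the denominator only.** Reported rate = dT / ENR = d(1 − s).

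**Case B: screen failures also counted as discontinued.** Reported rate = d(1 − s) + s.

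| s | ENR | Screen failures | Case A | Case B | SAF |
|---|---|---|---|---|---|
| 5% | 5,263 | 263 | 19.0% | 24.0% | 20.0% |
| 10% | 5,556 | 556 | 18.0% | 28.0% | 20.0% |
| 20% | 6,250 | 1,250 | 16.0% | 36.0% | 20.0% |

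For s = 10%: case A is 1,000 / 5,556 = 18.0%; case B is (1,000 + 556) / 5,556 = 28.0%. In case A the relative loss equals s whatever the value of d. At s = 2% it is small: 20% × 0.98 = 19.6%.

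**Which case applies.** The SAP has no numerator rule. SAP 9.7.1.2.1 defines screen failures as their own category and tabulates their reasons separately from the reasons for discontinuation, so case A is the natural reading.

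**Counting by patient number.** Two re-screens allow three consents and three numbers per person. If ENR were counted by number, and a share r of treated patients had one earlier failed number, the denominator would be T / (1 − s) + rT. With s = 10% under case A:
- r = 5%: 1,000 / (5,556 + 250) = 17.2%.
- r = 10%: 1,000 / (5,556 + 500) = 16.5%.

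These two figures apply only if numbers are counted, which the SAP does not state.

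**The case against.** The strongest reply is that this is a routine disposition table, not a safety endpoint. Neither Protocol 9.4 nor SAP 9.7.1.6.1 lists it among the primary safety assessments, and adverse events leading to discontinuation have their own tables. The study is single-arm and descriptive. The number discontinuing will be shown and the size of SAF will be known, so a reader could recompute the percentage. The size rests entirely on assumed rates. All of this is fair, and it limits the weight of the point. The recomputation, however, works only if the reader knows whether screen failures are in the numerator, and the SAP does not say.

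Four stronger readings are tempting, and the documents do not support them:

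- *The rate is certain to be too low.* The sentence concerns leaving the study, not stopping the drug, and Protocol 5.5.1 sends reasons for not being treated to a screening disposition form. Screen failures could be tabulated as discontinued, which would push the figure up.
- *ENR contains the same person several times.* ENR is defined by patients. Only the last screening reason is reported, and SAP 9.7.1.2.1 plans a listing that links each patient to the PARADIGM-HF number. A risk remains, because Protocol 5.5.1 identifies a patient by the ID number, Protocol 6.1 changes that number at re-screening, and no rule for removing duplicates is given.
- *This is the main tolerability measure.* The documents do not call it that. It is the only planned all-cause discontinuation rate by reason, which is a narrower statement.
- *It conflicts with adverse-event tables built on SAF.* SAF is named explicitly only for the registry tables. All-cause and adverse-event discontinuation also have different numerators, so they would differ even on one denominator.

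**Conclusion.** The point holds. The rule as written gives a percentage that is not a rate among treated patients, and no other planned table supplies all-cause discontinuation by reason in that group. The likely direction is downward, by a relative amount equal to the screen-failure share of ENR: an assumed 20% would read 19.0%, 18.0% or 16.0% at an assumed 5%, 10% or 20%. If screen failures were counted as discontinued, the 10% case would read 28.0%. A rule that allows 18.0% or 28.0% from the same data should be settled before the table is produced. Both the discontinuation rate and the screen-failure share are assumptions. Repeat numbers are a secondary counting risk.

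**What to change.** In SAP 9.7.1.2.1:

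- Compute the number, percentage and reasons for discontinuation in SAF.
- State that screen failures are not discontinuations.
- Use ENR only for the screening flow (screened, failed, treated), counting each person once by the PARADIGM-HF number. That number is already collected (Protocol 6.2).

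The cost is about one sentence in the SAP and a changed denominator in one table. No new data are needed, and no test or sample size changes. The reported discontinuation rate will probably be slightly less favourable.

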9.7.1.2.2 Patient demographics and other baseline characteristics

Demographics and baseline data at baseline (defined below) will be summarized in the safety set (SAF). Continuous variables will be summarized by using n, mean, median, standard deviation, minimum, maximum, and categorical variables will be summarized by using frequency and percentage.

Summary statistics will be provided for demographics and other baseline characteristics including:

- (continuous) Age (years)
- (categorical) Age group: <65 years, >=65 years, <75 years, >=75 years at Visit 1
- (categorical) Sex
- (categorical) Race
- (categorical) Ethnicity
- (continuous) Height (cm)
- (continuous) Body weight (kg)
- (continuous) BMI (kg/m**2)
- (continuous) Systolic blood pressure (SBP) mm/Hg
- (continuous) Diastolic blood pressure (DBP) mm/Hg
- (continuous) Pulse (beats/min)

Body mass index (BMI) will be calculated from the measurements of height (m) and body weight (kg) measured at Visit 1: BMI = weight / height².

Relevant medical history will be summarized by primary system organ class and preferred term using frequency tables for the safety set.

Demographic, background, and medical histories data will be listed for the safety set.

The above analyses will also be performed for the ENR.

9.7.1.3 Definitions of baseline, post-baseline, and unscheduled visit

Baseline

In general, based on the principle described in the protocol, the baseline measurement is defined as the available measurement at Study start/Visit 1.

Post-baseline

Any measurements taken after baseline will be considered as post-baseline measurements.

Unscheduled visit

Unscheduled visit measurements will be taken into account for the analysis of safety laboratory evaluation

9.7.1.4 Missing date handling

All patients with imputed date will be listed for date imputation validation.

9.7.1.4.1 Event date missing or partially missing

If the date of an event is not known or is incomplete, the imputation rules are:

- a) If the day of the event is unknown, then the 15th day of this month will be imputed for a missing day;
- b) If only the month is unknown, then July will be used for imputation of the missing;
- c) If only the year of the event is known, then the 1st of July will be imputed for a missing day and month;
- d) The above rules are only for general case. If there is additional information available for the missing date, then the information should be used and the imputation of missing date should be treated differently. For example, if an event occurs between two visits and its date is missing, then the date in the middle of these visits may be used.

9.7.1.4.2 Study drug stop date missing

If study drug stop date is unknown or is incomplete, the imputation rules are:

- a) If only the day field of the drug stop is missing, then the missing date is imputed by using the 15th of the month;
- b) If year and month are missing, then use the date of completion/discontinuation of the open-label treatment epoch if it is non-missing and no earlier than the start date of treatment;
- c) If the drug stop date is completely missing, then:
 - a. If patient had fatal AE (identified as either start or end date is equal to the date of death and the AE is flagged as an SAE), handling rules are (in the specified order):
 - i. AE end date is not missing: use the AE end date to replace the missing drug stop date;

- ii. AE end date is completely missing but AE onset date not missing: use the AE onset date to replace the missing drug stop date;
- iii. AE end date is partially missing (only day field is missing): use Novartis standard procedure to impute the AE end date, and then use the imputed AE end date to replace the missing drug stop date;
- iv. AE end date is completely missing and AE onset date is partial missing (missing the date field only): impute the AE onset date using Novartis standard procedure, and then use the imputed AE onset date to replace the missing drug stop date;
- v. If both the AE onset and end dates are completely missing then use the last previous non-missing visit date plus 35 days to replace the missing drug stop date.

b. If patients had no fatal AE, handling rules are the same with the case that year and month are missing.

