- its outcome (not recovered/not resolved; recovered/resolved; recovering/resolving, recovered/resolved with sequelae; fatal; or unknown)

All adverse events should be treated appropriately. Treatment may include one or more of the following: no action taken (i.e. further observation only); investigational treatment dosage adjusted/temporarily interrupted; study drug(s) permanently discontinued; concomitant medication given; non-drug therapy given. The action taken to treat the adverse event should be recorded on the Adverse Event CRF.

Once an adverse event is detected, it should be followed until its resolution or until it is judged to be permanent, and assessment should be made at each visit (or more frequently, if necessary) of any changes in severity, the suspected relationship to the investigational study treatment, the interventions required to treat it, and the outcome.

The Sponsor may request additional information on specific adverse events of interest and may make requests to perform additional diagnostic tests to further assess the safety profile of the study medications. Such information may include diagnostic procedure reports, discharge summaries, autopsy reports, and other relevant information that may help in assessing the reported adverse event. All additional information will be de-identified prior to collection by Novartis or its agents.

Information about common side effects already known about the investigational drug can be found in the Investigator Brochure (IB) or will be communicated between IB updates in the form of Investigator Notifications. This information will be included in the patient informed consent and should be discussed with the patient during the study as needed.

The investigator should also instruct each patient to report any new adverse event (beyond the protocol observation period) that the patient, or the patient's personal physician, believes might reasonably be related to study treatment. This information should be recorded in the investigator's source documents, however, if the AE meets the criteria of an SAE, it must be reported to the Sponsor.

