9.7.1.5 Study medication

9.7.1.5.1 Duration of treatment exposure

Duration of the treatment exposure (in days) will be summarized by using n, mean, standard deviation, minimum, Q1, median, Q3, maximum for the safety set.

The duration of the treatment exposure for a patient, regardless of temporary interruptions of usage of the study drug, is defined as

date of last study drug intake – first study drug date + 1.

The durations on each dose level, time from Visit 1 to the first dose of each dose level, and time from the first dose intake to the final top dose will also be summarized.

Duration of total exposure to study drug (excluding interruptions) will be computed as

- date of last study drug intake – first study drug date + 1 – *number of days of treatment interruption*.

The duration of total exposure to study drug will be summarized by using n, mean, standard deviation, minimum, Q1, median, Q3, maximum for the safety set.

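### SAP 9.7.1.4.2 rule (a) sets a missing drug-stop day to the 15th with no floor at treatment start and no cap at death, and two fatal-AE sub-rules in the same section can never apply

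*SAP*

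**What the plan says.** SAP 9.7.1.4.2 handles a missing or incomplete study-drug stop date in three rules.

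- Rule (a), only the day missing: "If only the day field of the drug stop is missing, then the missing date is imputed by using the 15th of the month". Neither first dose nor death is mentioned.
- Rule (b), year and month missing: the end date of the open-label epoch is used, "if it is non-missing and no earlier than the start date of treatment". This is the only lower bound written in the section. No fallback is given if the condition fails.
- Rule (c), stop date completely missing: if the patient had a fatal AE, the stop date is taken from that AE through sub-rules i to v; otherwise rule (b) applies. A fatal AE is "identified as either start or end date is equal to the date of death and the AE is flagged as an SAE".

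The stop date feeds SAP 9.7.1.5.1, where exposure is "date of last study drug intake – first study drug date + 1". A second version subtracts interruption days, and time on each dose level is also summarised. SAP 9.7.1.5.2 weights each patient's daily dose by days at each level. The exposure summaries include the minimum and maximum. For AEs, Protocol 7.1 collects an outcome whose categories end "recovered/resolved with sequelae; fatal; or unknown".

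**The concern.** The authors saw the need for a floor in rule (b) and, through it, in the no-fatal-AE branch of rule (c), but left it out of rule (a) and the fatal-AE branch. No rule has a cap at death. A programmer who follows rule (a) literally can produce stop dates before first dose or after death, and because the minimum is reported, one such patient shows in the table. Patients who stop soon after starting are the most exposed: the first titration visits fall 1 to 2 and 2 to 4 weeks after first dose (Protocol 5.5.4), so start and stop can share a calendar month.

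The fatal-AE branch has a different fault. Its entry test needs a complete AE date, yet two of its sub-rules are written for AEs that have none.

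**Working it through.** The SAP states no figure on this point, so its own formula is applied to dates imputed by its own rule. I take the imputed stop date to be the date of last intake.

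**1. First dose and stop in the same month, stop day missing.** Exposure = 15 - (first-dose day) + 1.

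| First-dose day | Exposure (days) |
|---|---|
| 15 | 15 - 15 + 1 = 1 |
| 16 | 15 - 16 + 1 = 0 |
| 20 | 15 - 20 + 1 = -4 |
| 31 | 15 - 31 + 1 = -15 |

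With 2 interruption days, the patient starting on the 20th has a total exposure of -4 - 2 = -6.

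**2. How many date pairs are affected.** Count every pair with first dose on or before stop in one month. A 30-day month has 30 × 31 / 2 = 465 pairs. Starts on days 16 to 30 contribute 15 + 14 + ... + 1 = 120, of which 15 give zero and 105 give negative exposure: 120/465 = 26%. A 31-day month gives 136 of 496 (27%), and a 28-day month 91 of 406 (22%). These are shares of date pairs, conditional on a missing day and a stop in the start month.

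**3. Dose-level durations.** If time on a level is computed in the same way (the SAP gives no formula), a patient moved to a new level on the 20th who stops that month has -4 days on it, even if first dose was months earlier.

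**4. Death in the stop month.** Days past death = 15 - (death day): 14 for a death on the 1st, 12 on the 3rd, 1 on the 14th. Example: first dose 10 January, death 3 May, stop recorded only as May (non-leap year). Exposure to 15 May is 126 days; to the date of death it is 114.

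**5. Fatal-AE sub-rules.** The entry test requires the AE start or end date to equal the death date.

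- Sub-rule iv (end date missing, onset partial) and sub-rule v (both missing) leave no complete date to match, so neither can be reached.
- A fatal AE with a complete but earlier onset and an incomplete end date fails the test and goes to the no-fatal-AE rule.
- A non-fatal SAE that happens to start or end on the day of death passes it.
- Sub-rule iii is reachable when onset equals death and only the day of the end date is missing. It then imputes an end date by a sponsor procedure not given here, although the death date is known. If that procedure also used the 15th (assumption), a death on the 3rd would again give a stop 12 days late.

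**6. Size for the mean.** The number of partial stop dates is not given. If 1% of patients were each shifted by +14 days (assumption), mean exposure would move by 0.01 × 14 = 0.14 day; at 5%, 0.7 day.

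**The case against.** Safeguards exist. SAP 9.7.1.4 lists every patient with an imputed date for validation. Protocol 8.2 and 8.3 provide automatic checks and queries. Dose changes and discontinuation are also registered in the IRT (Protocol 5.5.5, 5.5.9), and the SAP refers to a project-level harmonization plan that is not available here. Impossible dates would probably be noticed. That stands, but none of these texts states a bound or a correction, so any repair would be ad hoc.

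Several stronger readings are tempting, and the documents do not support them.

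- A reader might infer that the event-date rules in SAP 9.7.1.4.1 have the same fault, since "If only the year of the event is known, then the 1st of July will be imputed for a missing day and month". Rule (d) there says additional information should be used when available, and a known first-dose or death date can reasonably count as such. That rule is written for events, so it does not rescue rule (a) for stop dates.
- A reader might infer damage to patient-time rates or to treatment-emergent status. No exposure-adjusted rate is planned. SAP 9.7.1.6.1 counts patients with any AE during the study period; the treatment-emergent label appears only for the registry tables, with no date window.
- A reader might object to sub-rule v, "then use the last previous non-missing visit date plus 35 days to replace the missing drug stop date", as a poor fit to 6-month visits. As the test is written, the sub-rule is never reached and changes no result.
- A reader might blame date matching for zero or negative exposure. It operates only when the stop date is completely missing; rule (a) is the main cause.
- A reader might expect the average daily dose to fail through division by zero. That needs a patient's days to sum to exactly zero, for example a single dosing record starting on the 16th.

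**Conclusion.** Wrong as written, and minor. Rule (a) can yield an exposure of 0 to -15 days and a stop date 1 to 14 days after death, and it conflicts with the floor in rule (b). The 26% and 27% are not shares of patients: they apply only to stops in the start month with a missing day, and give every date pair equal weight. The patients affected are probably few. The effect falls on descriptive exposure and dose-duration summaries, chiefly the minimum, with a very small shift in the mean under the assumptions shown. Counts of AEs, including those leading to discontinuation, do not depend on the imputed stop date.

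The fatal-AE fault is separate and is one of logic: two sub-rules cannot apply, and some fatal AEs are handled as non-fatal although the outcome is collected.

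**What to change.** Replace rule (a) in SAP 9.7.1.4.2 with: imputed stop date = max(start of the latest dosing record, min(15th of the month, death date, discontinuation date)). The latest dosing record should be one with a non-zero dose, and never earlier than first dose. Apply the same two bounds to any date imputed under rule (c). Identify fatal AEs by the recorded outcome of fatal, with the known death date as the upper limit, and rewrite sub-rules i to v to match.

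Three notes on the formula.

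- The floor must be outermost. With first dose on the 20th and a discontinuation date wrongly recorded as the 18th, a floor placed inside the min gives 18 - 20 + 1 = -1 day; the form above gives 20 - 20 + 1 = 1 day.
- The floor should use the latest dosing record. With first dose on the 20th, interruption on the 22nd and 23rd and restart on the 24th, a floor at first dose gives 1 - 2 = -1 day of total exposure; a floor at restart gives (24 - 20 + 1) - 2 = 3.
- It removes impossible values but does not recover the true date. A patient who starts on the 16th and really stops on the 30th has 15 days of exposure and is recorded with 1. The listing already planned in SAP 9.7.1.4 can flag such cases.

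In the examples above, starts on the 16th, 20th and 31st each become 1 day, and 126 days becomes 114. The cost is a few SAP sentences and a small code change before database lock, with no new data.
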